4.6.3 Adverse Reaction

An adverse reaction is a subset of all suspected adverse reactions and is defined as any AE caused by a drug.

4.6.4 Adverse Device Effects

Adverse device effects are those AEs thought to be related to the use of an investigational medical device. This definition includes AEs resulting from insufficient or inadequate instructions for use, deployment, implantation, installation, or operation, or any malfunction of the investigational medical device. This definition also includes any event resulting from use error or from intentional misuse of the investigational medical device.

An Unanticipated Adverse Device Effect is an adverse device effect, which by its nature, incidence, severity or outcome has not been identified in available information on the device.

Additional device issues, malfunctions or misuse will be documented in the electronic CRF.

4.6.5 Serious Adverse Event Definitions / Reporting Requirements

4.6.6 Serious Adverse Event or Serious Suspected Adverse Reaction

An AE or suspected adverse reaction is considered serious if, in the view of either the Investigator or Sponsor, it results in any of the following outcomes:

Death. This includes any death that occurs while the subject is on study and/or within 30 days after the last dose of study drug. An autopsy will be requested, and if performed, results will be submitted to the Sponsor.

A life-threatening AE. An AE or suspected adverse reaction is considered life-threatening if, in the view of either the Investigator or Sponsor, its occurrence places the subject at immediate risk of death. It does not include a reaction that had it occurred in a more severe form, might have caused death.

Inpatient hospitalization or prolongation of existing hospitalization. In the absence of an AE, hospitalization or prolongation of hospitalization should not be reported as a serious AE (SAE) in the following situations:

Hospitalization or prolongation of hospitalization is needed for a procedure required by the Protocol.

Hospitalization or prolongation of hospitalization is part of routine procedure followed by study center.

Hospitalization for survey visits or annual physicals.

For a hospitalization planned (and documented) before the start of the study for a pre-existing condition which has not worsened.

A persistent or significant incapacity or substantial disruption of the ability to conduct normal life functions.

A congenital anomaly/birth defect.

Important medical events that may not result in death, be life-threatening, or require hospitalization may be considered serious when, based upon appropriate medical judgment, they may jeopardize the subject and may require medical or surgical intervention to prevent one of the outcomes listed in this definition. Examples include allergic bronchospasm requiring intensive treatment in an emergency room or at home, blood dyscrasias or convulsions that do not result in inpatient hospitalization, or the development of drug dependency or drug abuse.

4.6.7 Pregnancy

For safety reporting purposes, any pregnancy occurring during the study will be considered an “important medical event”. If a study subject becomes pregnant while participating in the study, the study drug will be discontinued immediately and the pregnancy will be reported to the Sponsor. The Investigator will then report follow-up information to the Sponsor regarding the course of the pregnancy, including perinatal and neonatal outcome, regardless of the fact that the subject has discontinued the study. Once the newborn is determined to be healthy, as defined by and agreed upon by the Sponsor and Investigator, additional follow-up will no longer be required.

4.6.8 Serious Unexpected and Suspected Adverse Reaction

An unexpected AE (or serious and unexpected suspected adverse reaction [SUSAR]) is any AE or suspected adverse reaction that is not listed in the IB or is not listed at the specificity or severity that has been observed, if an IB is not required/available, is not consistent with the risk information described in the general investigational plan. This also refers to AEs or suspected

adverse reactions mentioned in the IB as occurring with a class of drugs or as anticipated from the pharmacological properties of the drug but are not specifically mentioned as occurring with the study drug. A SUSAR requires mandatory expedited reporting to the applicable regulatory authority(ies). The Sponsor will forward the formal notification describing the SUSAR to Investigators. Each Investigator must then notify his/her IRB of the SUSAR, in accordance with the IRB's policy.

The Sponsor should be notified within 24 hours of the Investigator becoming aware of a SUSAR and the event documented on the CRF.

4.6.9 Recording Adverse Events

All AEs (including SAEs) within the 5 pre-surgery visits are to be accurately recorded on the AE/SAE page(s) of the CRF. In addition, any SAEs within 30 days of visit 5 will need to be recorded. The Investigator will carefully evaluate each AE to determine:

- Duration (start and end dates)
- Severity (grade)
- Seriousness
- Relationship to study drug (Not Related, Possible, Definite)
- Action taken (none, study drug modification, medical intervention)
- Outcome (resolved without sequelae, resolved with sequelae, ongoing)

The Investigator will evaluate all AEs and SAEs with regard to maximum intensity and relationship to study drug. Maximum intensity should be assigned using one of the severity grades as outlined in the NCI CTCAE v4.0. If the AE is not specifically listed in CTCAE v4.0, the following grades will be used:

- Grade 1: mild
- Grade 2: moderate
- Grade 3: severe
- Grade 4: life-threatening or disabling
- Grade 5: death

4.6.10 Determining Relationship of Adverse Events to Study Drug

The Investigator must attempt to determine if an AE or SAE is related to the use of the study drug. This relationship should be described as follows:

- Possible** The event follows a reasonable temporal sequence from administration of the study drug and the event follows a known response pattern to the study drug BUT the event could have been produced by an intercurrent medical condition which, based on the pathophysiology of the condition and the pharmacology of the study drug, would be unlikely to be related to the use of the study drug OR the event could be the effect of a concomitant therapy.
- Definite** The event follows a reasonable temporal sequence from administration of the study drug, the event follows a known response pattern to the study drug and

based on the known pharmacology of the study drug, the event is clearly related to the effect of the study drug.

Not Related Based on the evidence available, causality is not possible.

4.7 Adverse Events Analysis:

All treatment-emergent adverse events (TEAE) will be summarized. Counts and percents of each observed system organ class (SOC) and preferred term as defined in the Medical Dictionary for Regulatory Activities (MedDRA) version 9.0 or later will be presented. The preferred terms will be summarized in the following sets of tables:

- Baseline AEs, occurring after enrolment and prior to treatment;
- All TEAEs;
- All serious TEAEs;
- All TEAE leading to discontinuation from study
- All TEAEs by closest relationship (related or not related). Relationship will be recorded as definitely related, probably related, possibly related, or not related to the study medication; the recorded relationship will be included in listings.

Reported severity (mild, moderate or severe) will be included in the listing. The severity of the TEAEs will be graded according to the CTCAE criteria, version 4.0 (Appendix 3). A separate table for AE of CTCAE grade greater than 2 (moderate) will be generated. The severity of oral mucositis will be graded according to the WHO grade.

A subject having the same TEAE (preferred term) more than once over the course of the study will be counted only once in the incidence calculation for that preferred term. Similarly, if a subject had more than one TEAE in a single SOC, the subject will be counted only once in the incidence calculation for that SOC. If a subject had a TEAE more than once in the study, the occurrence with the maximum severity will be used in the calculation of the incidence of individual TEAE by severity. If a subject had a TEAE more than once in the study, the occurrence with the highest relationship to treatment will be used in the calculation of the incidence of individual TEAE by relationship.

4.7.1 Deaths, Other Serious Adverse Events (SAEs), and Other Significant AEs Analysis:

Listings will be provided for

- Deaths,
- SAEs,
- Discontinuations due to TEAEs,
- Grade 4 AEs, and
- Related AEs.

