# 7.4 Criteria for Individual Subject Discontinuation from the Trial

Subjects may withdraw from further participation in the study at any time and for any reason without prejudice. The degree to which a subject withdraws can vary and efforts will be made to collect important safety data if feasible and the subject agrees. A subject will be considered to be withdrawn from the trial for the following reasons:

- Withdrawn consent from all treatment and follow-up
- Death
- Lost to follow-up
- Termination of the trial by the Sponsor

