#### 8.4 Dose Interruption

At the Investigator's discretion, study drug may be interrupted, for reasons not related to toxicity (eg, intercurrent illness, subject scheduling conflict). Such interruption may not last more than 144 hours and may not occur more than 1 time during the subject's treatment schedule.

Subjects who experience an AE(s) requiring interruption of study drug for  $\geq$ 144 hours will be removed from treatment.

Subjects who experience a DLT will be terminated from dosing, but will remain in the study for the purpose of data collection. The DLT period will be defined as the start of treatment to 14 days after the last treatment application or the time of surgery, whichever is first.

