# 9.3.6.6 Recording Adverse Events

All AEs (including SAEs) within the 5 pre-surgery visits are to be accurately recorded on the AE/SAE page(s) of the CRF. In addition, any SAEs within 30 days of visit 5 will need to be recorded. The Investigator will carefully evaluate each AE to determine:

- Duration (start and end dates)
- Severity (grade)
- Seriousness
- Relationship to study drug (Not Related, Possible, Definite)
- Action taken (none, study drug modification, medical intervention)
- Outcome (resolved without sequelae, resolved with sequelae, ongoing)

The Investigator will evaluate the recorded AEs and SAEs with regard to maximum intensity and relationship to study drug. Maximum intensity should be assigned using one of the severity grades as outlined in the NCI CTCAE v4.0. If the AE is not specifically listed in CTCAE v4.0, the following grades will be used:

- Grade 1: mild
- Grade 2: moderate

- Grade 3: severe
- Grade 4: life-threatening or disabling
- Grade 5: death

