## 10.5.6 Safety Data

Safety observations and measurements including study drug exposure, AEs, laboratory data, physical examination findings, VS, weight, and concomitant therapy will be summarized and presented in tables and listings.

Laboratory parameters will be summarized using descriptive statistics and data listings. The incidence of clinically significant abnormalities will be summarized. Physical examinations, VS, and weight will be summarized by changes from baseline values using descriptive statistics.

AEs occurring after the start of treatment are TEAEs. The severity of the TEAEs will be graded according to the CTCAE criteria, version 4.03. The severity of oral mucositis will be graded according to the WHO grade (Section 8.2).

The number and percentages of subjects experiencing TEAEs will be tabulated by system organ class and preferred term. Assessments of TEAEs will include characterization of the type, incidence, severity, seriousness, and relationship to treatment. Summary subject listings will be provided for subjects with dose modification, SAEs, TEAEs resulting in study discontinuation, and deaths. The rates of local tolerability and oral mucositis will be reported.

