2.5 Criteria for Individual Subject Discontinuation of Protocol Therapy

Subjects should be discontinued from protocol therapy, while follow-up as per protocol, for the following reasons:

- Completion of the scheduled PRV111 therapy
- Meets 1 of the stopping rules for an individual subject
- Pregnancy
- Noncompliance with trial or follow-up procedures
- Withdrawal at the Investigator's request for any reason that the Investigator believes continuation of study drug therapy would not be in the subject's best interest
- Subjects may be withdrawn at any time for drug intolerability, disease progression, availability of other therapeutic options, or subject judgment

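### The planned adverse-event discontinuation table counts subjects who leave the study, so it would omit most subjects whose PRV111 dosing was stopped for an adverse event

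*SAP*

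**What the plan says.** **The outputs.** Among the TEAE tables in SAP 4.7, one concerns discontinuation: "All TEAE leading to discontinuation from study". Protocol 10.5.6 promises subject listings that include "TEAEs resulting in study discontinuation, and deaths", and SAP 4 repeats this. SAP 4.7.1 adds a listing of discontinuations caused by TEAEs, without saying whether drug or study is meant.

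**The rules for subjects.** Protocol 7.3 and SAP 2.5 deal with stopping therapy: "Subjects should be discontinued from protocol therapy, while follow-up as per protocol, for the following reasons". Toxicity belongs there. The SAP list includes "Meets 1 of the stopping rules for an individual subject", and both lists allow withdrawal for drug intolerability. Protocol 8.4 is explicit about DLTs: "Subjects who experience a DLT will be terminated from dosing, but will remain in the study for the purpose of data collection". The same section takes off treatment "Subjects who experience an AE(s) requiring interruption of study drug for" 144 hours or more.

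Leaving the trial is a separate matter, in Protocol 7.4 and SAP 2.6: "A subject will be considered to be withdrawn from the trial for the following reasons". The reasons are consent withdrawn for all treatment and follow-up, death, loss to follow-up, and termination by the sponsor.

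**The data.** The adverse-event record carries "Action taken (none, study drug modification, medical intervention") in Protocol 9.3.6.6, and SAP 4.6.9 has the same choices. Protocol 7.5 and SAP 2.7 separately require the reason for stopping dosing to be documented on the CRF.

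**The concern.** In a first-in-human trial, a safety reader expects the discontinuation table to say how many subjects could not continue the drug because of an adverse event. Here the table is tied to the wrong event. The plan's rules keep a subject who stops PRV111 for toxicity in the study, so that subject does not meet the table's criterion.

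The Protocol's primary objective is a safe and efficacious dose. A subject who stops before completing 3 of the 4 application visits also falls outside the Evaluable Population (SAP 5.2.2). An early stop for an adverse event that is not a DLT could therefore be missing from both the response analysis and the only discontinuation table.

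**Working it through.** The plan gives no figure to reproduce. The check compares the table's criterion with the rules that decide who meets it.

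| How dosing or participation ends | Status under the plan | In the SAP 4.7 table as written? | Specified count elsewhere? |
|---|---|---|---|
| Non-fatal DLT while treatment visits remain | Dosing ends, subject stays (Protocol 8.4) | No | Yes, DLT incidence (Protocol 10.5.3, SAP 2.12.1) |
| DLT arising after the last treatment visit | No dosing left to stop | No, and it would not belong in a drug-stop table either | Yes, DLT incidence |
| AE interruption of 144 hours or more, not a DLT | Off treatment; leaving the study not stated (Protocol 8.4) | No, unless the subject also leaves | None |
| Stop for intolerability or on the investigator's judgement because of an AE, not a DLT | Off therapy, follow-up continues (Protocol 7.3, SAP 2.5) | No | None |
| Fatal AE | Leaves (Protocol 7.4, SAP 2.6) | Yes | Deaths are listed |
| AE followed by withdrawal of all consent | Leaves | Yes, if the AE is recorded as the cause | None needed |
| AE-related withdrawal from the study (SAP 6.3) | Leaves | Yes | None needed |

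The third and fourth rows are the gap.

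**Can a stop for an AE fall outside the DLT count?** Yes, for two reasons.

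1. The interruption rule in Protocol 8.4 sets no grade, so a lower-grade event can end treatment.
2. The two documents define differently the DLT criterion for toxicity that prevents enough of the planned applications. Protocol 8.2 accepts any toxicity; SAP 2.10 requires grade 3 or 4 and a relation to the drug. A grade 2 event that ends dosing early may therefore not be a DLT under the SAP. It would also miss the separate SAP 4.7 table of events above grade 2.

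**Size.** If k of n treated subjects stop PRV111 for a non-fatal event and stay in follow-up, the drug-discontinuation rate is k/n and the planned table shows 0/n. The documents do not give k, so k = 1 is an assumption. The denominator is the Safety Population (SAP 5.3 and 5.3.1), meaning anyone with at least one patch applied.

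- Stage 1 with all 10 permitted subjects treated: 1/10 = 10%, shown as 0/10.
- Stage 1 with only 5 treated: 1/5 = 20%, shown as 0/5.
- Both stages at maximum enrolment, 10 + 21 = 31: 1/31 = 3.2%, shown as 0/31.

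**The case against.** The best defence is that the information survives elsewhere.

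- DLT incidence is part of the primary endpoint, tolerability is defined by the DLT proportion, and DLT counts drive the dose decisions. Nothing in the plan judges tolerability from the discontinuation table. This stands, and it confines the main gap to stops that are not DLTs.
- SAP 4.7.1 lists discontinuations caused by TEAEs, Grade 4 events and related events. Exposure is summarised, dose modifications are listed, and completion status is summarised by stage (Protocol 10.5.2, SAP 5.3.4). In a trial this small, listings are informative. This stands in part. The discontinuation listing does not say drug or study and gives no counts, and the disposition summary does not name a permanent stop of drug for an AE.
- Protocol 7.5 and SAP 2.7 describe subjects who withdraw for safety reasons. SAP 6.3 covers study withdrawal at the investigator's discretion and mentions withdrawals due to AEs. This stands: the table need not be limited to deaths and consent withdrawals. It does not bring in subjects who stop drug and remain.
- Protocol 8.3 treats fewer visits as a dose modification, so a permanent stop might be coded under that action-taken choice. That is plausible, but it would then be indistinguishable from a reduction.
- SAP 1 says the table shells will accompany the final version, and these might settle the meaning. They might, but the text they would implement says study.

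A reader might go further and infer that the correct table cannot be built at all. The documents do not support that, because the reason for stopping dosing must be on the CRF.

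**Conclusion.** The point holds as a defect in how a safety output is defined. As written, the SAP 4.7 table and the matching summaries in SAP 4 and Protocol 10.5.6 would omit most subjects whose PRV111 was stopped for an AE. The part with no specified summary is stops that are not DLTs. With one such subject, the understatement is 10 percentage points among 10 treated in Stage 1, within a range of 3.2 to 20 points over the denominators considered. This rests on an assumed count, on a literal reading of the table title, and on subjects staying in follow-up as the plan requires.

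Two stronger readings are tempting but not supported.

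- A reader might infer that every non-fatal DLT is hidden and that the regimen would therefore look better tolerated than it was. DLTs are reported under the primary endpoint, and the DLT period runs up to 14 days after the last application or to surgery (Protocol 8.4), so some DLTs stop no dosing.
- A reader might take two DLT stops among 11 subjects, 2/11 = 18%, as the size of the error. Eleven is the evaluable target at the final dose, not the Safety Population, and DLTs are the events already counted.

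The primary test, the dose decisions and the collected data are unaffected. The change should be made before the tables are produced.

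**What to change.** 1. In SAP 4.7, define the table as TEAEs leading to permanent discontinuation of PRV111, on the Safety Population and by dose. Apply the same definition to the summaries in SAP 4 and Protocol 10.5.6 and to the SAP 4.7.1 listing.
2. Show withdrawal from the study due to an AE as a separate line.
3. Identify cases from the reason for dosing discontinuation that Protocol 7.5 and SAP 2.7 already require on the CRF.
4. Add a choice for study drug permanently discontinued to the action-taken field in Protocol 9.3.6.6 and SAP 4.6.9, so that a stop can be told apart from a dose modification.
5. Reconcile the differing DLT criterion in Protocol 8.2 and SAP 2.10, because it decides which stops the DLT count already covers. Which version is right is for the sponsor to settle.

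Items 1 to 4 cost wording in two documents and one pick-list entry. They need no new visits or assessments and change no clinical stopping rule.

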4.8 Pharmacokinetics and Biodistribution Assessment

4.8.1 Pharmacokinetics Analysis:

Whole blood samples will be assessed for PK parameters and maximum concentration (C_{max}) during treatment period will be determined. PK parameters will be derived from the platinum concentrations obtained from Excite Pharma Services. Tumor and lymph node cis platinum content will be provided as well.

Summary statistics for PK data will be displayed for the following category: :

1. Tumor tissue
2. Lymph nodes
3. Blood
4. Residual Patch

C_{max} based on blood concentrations across patch treatment period as well as other summary statistics for each patient will be listed.

Systemic, tumor and lymph node (if available) platinum levels will be summarized using descriptive statistics. Analysis will be adjusted based on the number of patches applied per application (1 or 2) and total number of treatment visits.

5 Data Analysis and Statistical Considerations

Statistical analyses and summaries will be provided when all corresponding data is collected and processed, and the corresponding database portions are locked through this stage of the

study. All available data from post-operative visits for other subjects, if any, will be included. The final analysis including all available post-operative data will be performed when the last subject has reached the 6-month post-operative follow-up visit and the final database is locked.

Statistical tables, data listings and graphs will be prepared using SAS Version 9.1 or higher (SAS Institute, Cary, North Carolina, USA).

5.2 Treatment Analysis Guidelines

5.2.1 Efficacy Analyses

The primary efficacy analysis will be conducted after all evaluable subjects will have undergone their surgical ablation of the oral tumor, in addition to the interim analysis described below.

Note: All hypothesis tests will be performed at a 0.018 level.

5.2.2 Evaluable Population

All subjects who have **met the inclusion and exclusion criteria**, and have completed at least 75% of the total dose required for that stage will be included in the Evaluable Population*. This population will be used for the efficacy analysis. **Only subjects in the evaluable population will be assessed for tumor response.**

* 75% is defined as at least 3/4 patch application visits completed

